#### 9.5. Data analysis

All qualitative outcomes will be summarized by frequency and percentage. The quantitative outcome will be summarized by mean and SD if data is symmetric, otherwise median, and IQR. The outcomes will also be classified and compared across different demographic and relevant clinical factors. External validity will be assessed by t-test/ANOVA or chi-square test of indepdence depending on the nature of the outcome. However, observations will be generalized for the population the selected patients would represent. p-value<0.05 will be considered statistical significance. A standard statistical software will be used for data analysis.

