#### 9.7. Limitations of the research methods

- The medical records may not be available for each & every data points provided in the CRF, from the aspect of the clinician or the patient.
- Patients may be lost to follow-up due to the occurrence of AEs, lack of efficacy or other reasons.
- This could be due to censoring events, that is, information on time to outcome event may not available for all study participants. Patient/s in such cases will be marked as "censored" when such information on time to event is not available due to loss to follow-up or non-occurrence of outcome events before the end of the study.
- For such patients (censored because of lost to follow-up due to the occurrence of AEs, lack of efficacy or other reasons), the use of Kaplan-Meier curves will be obtained as estimates of median OS, RFS and time to CR/Cri taking into account patients' attrition.
- The interpretation of data collected retrospectively will be dependent on the completeness and quality of the medical records and the reliability of the abstraction of data from the medical records. However, Source data verification (SDV) will be employed to identify and correct abstraction errors.

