# 3.2 STATISTICAL DECISION RULES

As no specified hypothesis will be tested, no decision rule are required to specify. However, for any assessment of external validity for a suitable population accepted false positive rate will be 5%. For any such validation only two sided test will be performed.

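### Protocol 9.5 names only t-test/ANOVA and chi-square, does not exempt time-to-event outcomes, and neither document names a censoring-aware comparison; DOR and 6/12-month survival also lack an explicit Kaplan-Meier plan

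*Protocol*

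**What the plan says.** Protocol 9.5 announces group comparisons: "The outcomes will also be classified and compared across different demographic and relevant clinical factors". That sentence names no test. The next one does, with external validity as its subject, to be assessed "by t-test/ANOVA or chi-square test of indepdence depending on the nature of the outcome". The section then sets the threshold, "p-value<0.05 will be considered statistical significance". Its summary rule is "The quantitative outcome will be summarized by mean and SD if data is symmetric, otherwise median, and IQR". Censoring is not mentioned in 9.5.

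Censoring appears in Protocol 9.7, which marks patients who are lost or event-free as censored and says "the use of Kaplan-Meier curves will be obtained as estimates of median OS, RFS and time to CR/Cri". DOR and the 6- and 12-month survival rates are not in that list.

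The SAP on the same points:
- 3.1 states no hypothesis. 3.2 limits testing: "for any assessment of external validity for a suitable population accepted false positive rate will be 5" per cent, and "For any such validation only two sided test will be performed".
- 7.1 and 7.2 plan Kaplan-Meier curves for OS and RFS, and median or restricted mean survival by number of prior salvage therapies. 7.2.2 item 13 adds restricted RFS time with 95% CI, overall and by HSCT status.
- 7.2, 7.2.2 item 7 and section 8 summarise DOR by median and IQR. 5.1 measures it as the time from start of InO to CR/CRi.
- Section 5 lists survival at 6 and 12 months as a secondary endpoint. No analysis section or table says how those two rates are computed.

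A log-rank test, a Cox model and a rank test appear in neither document.

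**The concern.** Protocol 9.5 promises comparisons of the outcomes in general and gives a significance level. An analyst looking for the method finds only tests that need fully observed data. OS, RFS and DOR are times that will be censored for some patients. A t-test or ANOVA on observed times treats the last contact of a living patient as that patient's death or relapse, so a group that is lost earlier looks as if it does worse. A chi-square test on alive or not at 6 or 12 months has the same difficulty with patients lost before the landmark.

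Two smaller gaps sit beside this. Section 9.5 recognises skewed data by switching to median and IQR, but offers no matching test. A plain median and IQR for DOR treats a remission that is still continuing at last contact as one that has ended.

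At stake is whether a difference in completeness of follow-up could be reported, at p<0.05, as a difference in survival.

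**Working it through.** The plan has no figure of its own to reproduce: the sample size rests on availability, with no power or event count. The check asks how far a t-test on observed times would go wrong when true survival is identical.

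**Inputs from the documents**
- N = 32 (administrative change letter), taken as 16 v 16. The equal split is an assumption.
- Median OS of 7.7 months and 23% alive at 2 years for InO (Protocol section 7).
- Index dates February 2017 to February 2022; data collection 13 February to 05 July 2023. Potential follow-up therefore runs from about 12 months (17 if records are read at the end of collection) to 77 months.

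**Assumed survival shapes**
- Exponential: λ = ln 2/7.7 = 0.0900 per month. S(24) = exp(−24 × 0.0900) = 11.5%, which is below the cited 23%.
- Mixture with 20% long-term survivors: 0.2 + 0.8·exp(−7.7λ) = 0.5 gives λ = −ln(0.375)/7.7 = 0.127. S(24) = 0.2 + 0.8·exp(−24 × 0.127) = 24%, close to the cited figure.

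**False-positive rate, 16 v 16, identical survival** (Welch t-test on min(event, censoring) unless noted; two-sided 5%; 3,000 to 4,000 runs). With 3,000 runs the Monte Carlo standard error is √(0.05 × 0.95/3000) = 0.4 points at 5%, and 0.65 points at 15%.

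| Assumed follow-up | t-test | log-rank |
|---|---|---|
| Same follow-up, no other loss | 4–5% | 5–6% |
| Loss by 12 months 5% v 40%, exponential | 11–13% | 5–6% |
| Loss by 12 months 5% v 40%, mixture | 15% | 5–6% |
| Complete split by era (12–42 v 42–77 or 17–47 v 47–77 months), exponential | 4–5% | about 6% |
| Complete split by era, mixture | 9–13% | 5–6% |
| Partial split by era (30% v 70% early patients), mixture (t-test variant not recorded) | 6.1% | 5.8% |

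Heavier early censoring in one group raises the t-test further (exponential survival, other group censored over 17–77 months): 20% with censoring uniform over 1–24 months, and 63% over 1–12 months. The log-rank test stays at 5%. Nothing in the documents indicates loss of that size.

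**12-month survival by crude percentage** (exponential; 20% lost by 12 months, assumed)
- True value: exp(−12 × 0.0900) = 34.0%.
- Loss hazard: μ = −ln(0.8)/12 = 0.0186.
- Known alive at 12 months: 0.3395 × 0.8 = 0.2716.
- Lost alive before 12 months: μ/(λ+μ) × [1 − exp(−12(λ+μ))] = 0.1712 × 0.7284 = 0.1247.
- Lost patients counted as alive: 0.2716 + 0.1247 = 39.6%.
- Lost patients dropped: 0.2716/(1 − 0.1247) = 31.0%.

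The crude figure is therefore about 6 points too high or 3 points too low, depending on a rule that the plan does not state. Kaplan-Meier is centred on 34% if loss is unrelated to prognosis. Almost every patient has at least 12 months of potential follow-up, so only loss to follow-up matters here.

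**The case against.** A reader might infer that OS and RFS will be compared as if every patient had reached the event. The documents do not say that. The sentence naming t-test/ANOVA has external validity as its subject. Protocol 9.7 censors and uses Kaplan-Meier. SAP 7.1, 7.2 and 7.2.2 plan Kaplan-Meier curves, and restricted mean or median times by salvage line or HSCT status, and list no t-test or ANOVA on any survival time. SAP 3.1 and 3.2 test no hypothesis outside external validity, and 7.2 puts magnitude first and makes interpretation qualitative. In a descriptive study, estimates with confidence intervals and no test are legitimate. All of this stands, and it rules out the strong reading.

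A reader might also infer that the spread of index dates alone would create false survival differences. It hardly does: the excess needs a factor that nearly separates patients by calendar era, together with long-term survivors, and nothing in the documents ties Ph status, age or prior lines to era. Nor does any passage say that 6- and 12-month survival will be crude percentages; the planned OS curve could supply the overall rates.

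The wording gap remains. No external population is specified for an external-validity test, and ANOVA and a test of independence are tests across groups, so an analyst could well take that sentence as the method for the comparisons announced just before it. If not, 9.5 announces comparisons and a threshold with no method. Either way, time-to-event outcomes are not exempted. The descriptive label does not resolve DOR, whose stated summary ignores censoring.

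**Conclusion.** The point holds as a minor gap in specification. Protocol 9.5 should not leave t-test/ANOVA and chi-square as the only named tests without excluding censored outcomes. DOR and the 6/12-month rates need an explicit censoring-aware method. Skewed, fully observed data need a rank test if they are tested at all.

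The size is conditional on a t-test actually being run on observed times, which the plan does not state. On that condition the false-positive rate is about 11–15% against 5–6% for the log-rank test, with 16 v 16 patients and 5% v 40% loss by 12 months. It stays near 5% when follow-up is similar. The loss rates, group sizes and survival shapes are assumptions, and the 5% v 40% contrast is fairly extreme. The estimation of OS and RFS is not in question.

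**What to change.** In Protocol 9.5 and SAP 7.1/7.2:
1. State that t-test/ANOVA and chi-square do not apply to OS, RFS, DOR or 6/12-month survival.
2. For groups fixed at baseline (salvage line, Ph status, disease burden, age), compare OS and RFS by two-sided log-rank test or by difference in restricted mean time with 95% CI, or declare these comparisons descriptive. Transplant status arises after the index date, so this item does not cover it.
3. Report 6- and 12-month survival by Kaplan-Meier with 95% CI.
4. Define DOR among responders, from the date of remission, with a censoring rule, and report it by Kaplan-Meier with 95% CI. Reconcile this with SAP 5.1, which measures time to CR/CRi under that name, and replace the median/IQR entries in SAP 7.2, 7.2.2 and section 8.
5. Use Wilcoxon or Kruskal-Wallis for fully observed variables summarised by median and IQR.

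The cost is wording. Event and last-contact dates are already needed for the planned OS and RFS curves; DOR also uses the date of remission, which the planned time-to-CR/CRi estimate already requires.

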### 9.1.3. Primary endpoint

Complete remission or complete remission with incomplete hematological recovery following treatment with InO, by the number of salvage therapies  $(0, 1, \ge 2)$  received before InO initiation.

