#### All these parameters will be assessed in the following subgroups -

- 1st salvage and later lines
- High burden and Low burden disease (<50%; 50-90%; >90%)
- Ph +ve and Ph ve patients
- Elderly patients> 65 years

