#### This PACL makes the following changes:

	izer		
3	6. MILESTONES	Change in Milestones- Planned Date	Start of data collection - 13 February 2023 End of data collection - 05 July 2023 Final Study report - 10 October 2023
4	9. RESEARCH METHODS 9.3 Study size	Sample size changed to 32 subjects	Sample size is changed to 32 subjects
5	11. MANAGEMENT AND REPORTING OF ADVERSE EVENTS/ADVERSE REACTIONS 12. SAFETY REPORTING	To clarify the adverse event reporting requirements for structured and unstructured data components. Also, to correct the inconsistency with the protocol template language.	The last 2 paragraphs of Section 11 should be moved to the beginning of Section 12, Adding a subheading "12.1 Structured Data Analysis", under which the 2 paragraphs are pasted and revised. In addition, add a second sub- heading "12.2 Human Review of Unstructured Data" above the original content of Section 12.

In the event that this protocol requires substantial changes that apply globally to all sites in the future or regulatory authorities request that these changes be incorporated into an updated protocol, the administrative changes described in this letter will be incorporated into the amended protocol.

Please inform your institutional review board/ ethics committee of these changes, as required.

Sincerely, [name]

cc: NI study master file

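### Protocol 9.5 names only chi-square for categorical outcomes; at 32 patients its expected-count condition fails, and p<0.05 is unreliable if small, uneven subgroups are tested

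*Protocol*

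**What the plan says.** Protocol 9.5 states that "The outcomes will also be classified and compared across different demographic and relevant clinical factors". The next sentence, on external validity, offers a t-test or ANOVA, or a "chi-square test of indepdence depending on the nature of the outcome", and the section later adds that "p-value<0.05 will be considered statistical significance". Neither document mentions an exact test, a continuity correction or a rule for small expected counts.

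Item 4 of the Protocol Administrative Change Letter says "Sample size is changed to 32 subjects". The letter lists no change to 9.5.

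The primary endpoint in Protocol 9.1.3 is "Complete remission or complete remission with incomplete hematological recovery following treatment with InO, by the number of salvage therapies", in three groups (0, 1, 2 or more). The list after Protocol 9.1.4 asks for all parameters by salvage line, disease burden (three levels), Ph status and "Elderly patients> 65 years".

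The SAP names no test. SAP 3.2 says there is no hypothesis, but that "for any assessment of external validity for a suitable population accepted false positive rate will be 5" per cent, two-sided. SAP 7.1 compares CR/CRi across salvage groups using 95% confidence intervals, without naming the interval method.

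**The concern.** Pearson's chi-square relies on a large-sample approximation. The usual condition is that no more than 20% of expected counts are below 5 and none is below 1. With 32 patients, three salvage groups and several further subgroup splits, many tables will be sparse. The p-value can then be well away from its nominal level. If an analyst applies 9.5 as written, a subgroup difference resting on one or two patients could be reported as statistically significant, and the 5% false positive rate in SAP 3.2 would not be met.

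**Working it through.** The plan has no figure to reproduce: 32 is an availability number, and Protocol 9.3 declines a power calculation.

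**Inputs.** N = 32 (change letter, item 4). Response rate 81%, so 19% non-response (the phase 3 InO result cited in Protocol section 7). Three salvage groups (Protocol 9.1.3). Two-sided 5% level (Protocol 9.5, SAP 3.2). Group sizes and event rates for VOD and organ toxicity are not given, so they are assumed and ranged.

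**1. Primary table.** Expected count = row total × column total / N.
- Expected non-responders: 32 × 0.19 = 6.08, or 2.03 per group on average.
- A non-responder cell reaches 5 only if its group has at least 5/0.19 = 26.3 patients, so 27.
- If no group is that large, all three non-responder cells are below 5: 3 of 6.
- If one group has 27 or more, the other two share at most 5 patients. Neither has more than 4, so all four of their cells are below 5: 4 of 6.
- None of the 85 possible splits therefore meets the 20% condition. Nor does any split at response rates of 20%, 29% or 40%. At 50%, 2 of 85 do.
- At N = 55 and 81% there are 55 × 0.19 = 10.45 expected non-responders, and none of 252 splits passes. The cut to 32 worsens the problem but did not create it.

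**2. Two-group tables with few events.** The smaller expected event count is largest in an even split. With 9 events it is 9 × 16/32 = 4.5. So 9 or fewer events (28% of 32 or less) always leave an expected count below 5.

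**3. True size of uncorrected Pearson on the primary table.** All outcomes were enumerated under equal 81% response:

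| Split | True size at nominal 5% |
|---|---|
| 11/11/10 | 4.0% |
| 4/14/14 | 4.6% |
| 2/15/15 | 4.8% |
| 2/20/10 | 5.1% |
| 1/15/16 | 7.3% |
| 1/3/28 | 8.1% |

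Over all 85 splits the range is 3.8% to 8.1%. Single tables can still mislead: in a 2/15/15 split with 6 non-responders, moving one patient (1/2/3 to 2/2/2) takes Pearson p from 0.45 to 0.0098, while the exact p for 2/2/2 is 0.0545.

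**4. One event in the smaller of two groups, none in the other.** Here chi-square = 32 × (32 − n)/(31 × n), and Fisher p = n/32 for these group sizes.

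| Split | Pearson p | Yates p | Fisher p |
|---|---|---|---|
| 3 v 29 | 0.0016 | 0.157 | 0.094 |
| 4 v 28 | 0.0072 | 0.249 | 0.125 |
| 5 v 27 | 0.018 | 0.336 | 0.156 |
| 6 v 26 | 0.034 | 0.416 | 0.188 |
| 7 v 25 | 0.055 | 0.489 | 0.219 |

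For 6 v 26: 32 × 26/(31 × 6) = 4.47, p = 0.034. With three groups, one event is enough only if the affected group has 4 or fewer (p = 0.027 at 4).

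**5. True size in two-group tables, assumed 5% event rate, N = 32.**

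| Split | Pearson | Fisher |
|---|---|---|
| 3/29 | 8.5% | 0.6% |
| 4/28 | 5.4% | 0.8% |
| 5/27 | 7.0% | 0.7% |
| 6/26 | 8.2% | 1.0% |
| 12/20 | 0.8% | 0.7% |
| 16/16 | 0.6% | 0.1% |

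Pearson is too liberal in small, uneven groups, only slightly so at 4/28. In even splits it hardly ever rejects.

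**The case against.** The chi-square sentence is about external validity, and the sentence on comparing outcomes names no test. SAP 3.2 limits its 5% rule in the same way. SAP 7.1 and 7.2 plan the primary comparison with confidence intervals only, and Grade 3/4 events as counts and percentages. SAP 7.2 ranks magnitude above statistical interpretation and asks for a qualitative reading. SAP 4.4 makes subgroup analysis conditional on meaningful representation, which would plausibly exclude a group of 3. Every inflated figure above also assumes the uncorrected statistic; with Yates' correction only a one-patient group reaches p<0.05 from a single event.

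Most of this stands, and it limits the point to a minor one. It does not remove it. Chi-square directly follows the plan to compare outcomes, is chosen by type of outcome, and is the only test offered to the analyst. The p<0.05 rule in 9.5 is not confined to external validity. SAP 4.4 sets no minimum group size. Neither document says that a correction applies, and Yates' correction does not extend to a three-group table.

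A reader might infer that 9.5 prescribes chi-square for the primary endpoint and so invalidates its analysis. The documents do not support that, because the SAP plans no p-value there.

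**Conclusion.** The point holds in limited form. The expected-count condition fails for every CR/CRi by salvage table at 81% response and N = 32, and for every two-group table with 9 or fewer events. Breaking that rule of thumb does little harm on the primary table unless one salvage group is tiny. Harm is material only if small, uneven subgroups with few events are tested without correction. One patient can then decide significance in a group of 6 or fewer, and true size reaches about 7% to 8.5% at 3, 5 or 6 patients (5.4% at 4).

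This rests on assumed group sizes and event rates, the uncorrected statistic, and the cited 81% carrying over. The denominator for CR/CRi in Protocol section 3 (patients with a recorded discontinuation date) could be below 32, which would make the cells smaller.

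Two stronger readings are tempting. One is that every toxicity table is sparse; the documents give no VOD or Grade 3/4 rate, and hematological toxicities need not be rare. The other is that a single patient can generally produce significance; that needs a small group. Severity is minor.

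**What to change.** - **Protocol 9.5:** state that Fisher's exact test (Freeman-Halton for more than two groups, mid-P version allowed) replaces chi-square whenever any expected count is below 5.
- **SAP 7.1:** no test is named there, and none need be added. State only that the 95% intervals for CR/CRi by salvage group, and for other proportions, are exact or Wilson intervals shown with the counts.

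The cost is one sentence in each document; standard software suffices and no new data are needed. The statistical downside is real. Fisher's size was about 1% or less in the sparse tables above, so some borderline differences will no longer be called significant. The change removes false positives in uneven groups but does not restore sensitivity in even splits with rare events, where Fisher (0.7% at 20/12) is no better than Pearson (0.8%). Mid-P is less conservative, but it halves the single-event p-value, so one event in a group of 3 would still give 0.094/2 = 0.047. The choice between Fisher and mid-P should therefore be fixed before analysis.

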#### 9.6. Quality control

## 9.6.1. Monitoring and Quality Control:

#### Insignia representative or delegate will:

Establish the adequacy of the facilities and the investigator's capability to appropriately select the sample.

Discuss with the investigator(s) (and other personnel involved with the study) their responsibilities with regard to protocol compliance, and the responsibilities of Insignia or its representatives. During the study, the Insignia representative or delegate can implement different activities to assure compliance with Insignia's standards of quality. These activities could include but are not limited to:

#### Contacts with the sites to:

Provide information and support to the investigator(s).

Ensure that the research team is complying with the protocol and that data are being accurately recorded in the CRFs.

Ensure that the CRFs are completed properly and with adequate quality.

Post-entry pre-analysis data validation will be performed, and if any information is missing or incorrect, the sites will be contacted.

#### Monitoring activities for:

Checking that patients exist in medical records (a sample)

The extent and nature of monitoring will be mutually decided. If the study in charge is suspicious of a potential non-optimal level of protocol compliance by the site investigator, specific measures should be adopted to evaluate the situation, identify the issue and implement specific action plans to correct the situation.

### 9.6.2. Reporting and Publication of Data:

Insignia will prepare a Study report within 2 months after the completion of the last patient. If a report of the study is published, the contribution of participating doctors will be duly acknowledged.

Insignia is obliged to analyze and report all study data as described in the protocol.

In accordance with the Declaration of Helsinki, both authors and publishers have ethical obligations. In publication of the results of the study, the authors are obliged to preserve the accuracy of the results. Negative as well as positive results should be published or otherwise publicly available. Insignia endeavors to publish the results of study and is committed to ensure that the data are reported in a responsible and coherent manner.

Insignia seeks to ensure that publications in biomedical journals follow the guidelines established by the International Committee of Medical Journal Editors (ICMJE) and published in its Uniform Requirements of Manuscripts Submitted to Biomedical Journals.

Insignia is committed to ensuring that authorship for all publications should comply with the criteria defined by the ICMJE. These state that: "Each author should have participated sufficiently in the work to take public responsibility for the content."

